For each patient, the study will consist of a period of 42 months which can include: an induction treatment period (approximately 6 months) followed by a maintenance treatment period (approximately 24 months) and a follow-up period of one year, after the last Obinutuzumab administration. Patients will be followed for 3.5 years after the first treatment administration regardless of early discontinuation of treatment for any reason in any time point. Patients who discontinue treatment for reasons other than disease progression (e.g., toxicity, AE) will continue to have their data collected for tumor assessments performed as per clinical practice, until disease progression,

withdrawal of consent, study termination by the Sponsor, or death, whichever occurs first, regardless of whether patients start a new anti-cancer therapy.

Start Date of Study:

The study start date will be the date of the first data collection: the date from which information on the first study patient is recorded in the study database. The planned start date is July 2019.

End of Study

The end of the study will be the date from which the last information of the last patient *still in the study* is recorded in the study database. The planned end date is December 2024.

Length of Study

This study will last approximately 5 years.

Target Population

Patients must meet the following criteria for study entry:

1. Signed Informed consent according to local regulations, after performing at least 2 cycles of induction treatment with Obinutuzumab and chemotherapy, within 1 year from beginning of treatment;
2. Age \geq 18 years.

Patients who meet any of the following criteria will be excluded from study entry:

1. Any contraindications to Obinutuzumab therapy according to local label for specific indication;
2. Concomitant participation in an interventional clinical study;
3. Patients not receiving treatment for untreated follicular lymphoma with Obinutuzumab according to standard of care and in line with the current summary of product characteristics (SmPC)/local labeling.

Studied Medicinal Product

The studied medicinal product is Obinutuzumab, an anti CD20, type II, monoclonal antibody that will be administered via intravenous (IV) infusion according to the SmPC (see Synopsis Table 1), in association with a chemotherapy regimen, during induction, and alone during maintenance treatment:

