- Time to response, defined as the time from first dose of Obinutuzumab to first documented response as assessed in clinical routine. Patients without response at the time of analysis and patients who are lost to follow-up will be censored at the date of their last tumour assessment. Patients without post-baseline tumor assessments will be censored at the time of their baseline visit unless death occurs prior to their first scheduled tumor assessment;
- Rate of patients with stable disease (SD);
- Effectiveness of Obinutuzumab in different patient subgroups, stratified by FLIPI (intermediate/high), ECOG-PS, age at study entry, hepatitis infection (history of past/resolved infection or latent HBV after prophylaxis as per standard treatment guidelines), chemotherapy backbone, presence of autoimmune disease, history of renal failure and liver failure;
- FDG-PET response at end of induction and end of maintenance, as per clinical practice. When PET is not performed, the alternative routine tumor assessment method will be collected.

Safety Variables

- Incidence, nature, seriousness, severity and relatedness of all adverse events (AEs) and serious adverse events (SAEs);
- Infusion related reactions (IRRs) management at each center as per clinical practice;
- Clinical laboratory abnormalities;
- Adverse events of special interest (AESI);
- Vital signs.

Other Variables of Interest

- Patient/disease characteristics: age, sex, ECOG PS, Ann Arbor staging, FLIPI (intermediate/high), medical history and history of FL, comorbidities, physical examination and vital signs;
- Treatment pattern:
 - Time from diagnosis to start of treatment with Obinutuzumab;
 - Duration of treatment with Obinutuzumab;
 - Dose modifications;
 - Treatment discontinuation;
 - Prophylaxis medications;
 - Type of chemotherapy chosen in association with Obinutuzumab;
 - Second line regimens prescribed for patients who progressed within two years after starting first line therapy;
 - Time to initiation of subsequent systemic anti-lymphoma therapy following initiation of Obinutuzumab containing therapy;
 - Adherence to treatments.
- Quality of life: EuroQol 5-Dimension Questionnaire, 5-level version (EQ-5D-5L); Functional Assessment of Chronic illness Therapy-Lymphoma (FACT-Lym);
- Presence of B symptoms;

- Concomitant medication prescribed or in current use from the start of therapy with Obinutuzumab until discontinuation of the treatment.

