For each patient, the study will consist of a period of 42 months which can include: an induction treatment period (approximately 6 months) in which patients will receive Obinutuzumab and chemotherapy followed by a maintenance treatment period (approximately 24 months) in which patients will receive Obinutuzumab monotherapy and a follow-up period of one year, after the last Obinutuzumab administration. Patients will be followed for 3.5 years after the first treatment administration regardless of early discontinuation of treatment for any reason in any timepoint. Patients who discontinue treatment for reasons other than disease progression (e.g., toxicity, AE) will continue to have their data collected for tumor assessments performed as per clinical practice, until disease progression, withdrawal of consent, study termination by the Sponsor, or death, whichever occurs first, regardless of whether patients start a new anti-cancer therapy.

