Appendix 3.2 Assessment of Causality of Adverse Events

For patients receiving combination therapy, causality will be assessed individually for each of the medicinal products.

Physicians should use their knowledge of the patient, the circumstances surrounding the event, and an evaluation of any potential alternative causes to determine whether or not an AE is considered to be related to the study medicine, indicating “yes” or “no” accordingly. The following guidance should be taken into consideration:

Temporal relationship of event onset to the initiation of study medicine

Course of the event, considering especially the effects of dose reduction, discontinuation of study medicine, or reintroduction of study medicine (when applicable)

Known association of the event with the study medicine or with similar treatments

Known association of the event with the disease under study

Presence of risk factors in the patient or use of concomitant medications known to increase the occurrence of the event

Presence of non-treatment-related factors that are known to be associated with the occurrence of the event

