3.3.1 Adverse events

Adverse events are those with start date beyond or equal to the date of first administration of Obinutuzumab and until 185 days after the last Obinutuzumab dose intake or until starting a new anti-cancer therapy (whichever occurs first). After this period AEs that are believed to be related to prior study drug treatment will be collected.

All adverse events will be assigned to a Preferred Term (PT) and will be classified by primary System Organ Class (SOC) according to the MedDRA thesaurus version 22 or higher. Summary statistical tables including frequency counts and percentages and the number of adverse events will be produced.

Data will be listed by study site, patient number, and study day. Events occurring on or after treatment on Day 1 (treatment-emergent adverse events - TEAEs) will be summarized by mapped term, appropriate thesaurus levels, and NCI CTCAE v5.0 grade. In addition, SAEs, including deaths, will be listed separately and summarized.

AEs leading to treatment discontinuation will be listed.

Infusion related reactions (IRRs) and adverse events of special interest (AESI) will be summarized by descriptive statistics and will be listed.

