- Results regarding effectiveness of Obitunuzumab in patient subgroups

Output for safety analyses

- Summary of Adverse Events and IRRs
- Listing of Adverse Event and IRRs
- Summary of clinical laboratory abnormalities during the study
- Summary of vital signs during the study

Output for exploratory analyses

- Summary of treatment pattern

- Summary regarding method applied to tumour response evaluation (e.g. FDG-PET)
- Summary about quality of life information from questionnaire
- Summary of presence of B symptoms during the study
- Summary regarding effectiveness in off-labels
- Summary regarding COVID19 impact on therapy maintenance
- Summary of concomitant medication
- Listing of concomitant medication

Appendix 3

Tables template for second interim analysis

Certificate Of Completion

Envelope Id: 91E6F38C07BF47F3875A27846F3045AE Status: Completed

Subject: Please DocuSign: StatisticaAnalysisPlan - URBAN - Vers 2 TB signed.pdf

Source Envelope:

Document Pages: 22 Signatures: 1

Certificate Pages: 4 Initials: 0

AutoNav: Enabled

Enveloped Stamping: Disabled

Time Zone: (UTC+01:00) Amsterdam, Berlin, Bern, Rome, Stockholm, Vienna

Envelope Originator:

[name]

[name]

IP Address: [REDACTED]

Record TrackingStatus: Original Holder: [REDACTED] Location: DocuSign
2/1/2022 5:48:48 PM [REDACTED]**Signer Events****Signature****Timestamp**[REDACTED]
[REDACTED]
Sent: 2/1/2022 5:50:10 PM
Viewed: 2/1/2022 5:50:59 PM
Signed: 2/1/2022 5:58:03 PM

Roche S.p.a.

Security Level: Email, Account Authentication
(Required), Login with SSO

Signature Adoption: Pre-selected Style

Signature ID:
053BD39F-A252-4544-A364-2F873F26579C
Using IP Address: [REDACTED]

With Signing Authentication via DocuSign password

With Signing Reasons (on each tab):

I approve this document

Electronic Record and Signature Disclosure:

Accepted: 9/25/2020 9:38:56 AM

ID: 196c6b45-7c21-4ab0-abea-47e4a6c71082

Company Name: F.Hoffmann-La Roche Ltd. - CFR Part 11 - Sub 1

In Person Signer Events	Signature	Timestamp
Editor Delivery Events	Status	Timestamp
Agent Delivery Events	Status	Timestamp
Intermediary Delivery Events	Status	Timestamp
Certified Delivery Events	Status	Timestamp
Carbon Copy Events	Status	Timestamp
Witness Events	Signature	Timestamp
Notary Events	Signature	Timestamp
Envelope Summary Events	Status	Timestamps
Envelope Sent	Hashed/Encrypted	2/1/2022 5:50:10 PM
Certified Delivered	Security Checked	2/1/2022 5:50:59 PM

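### The planned adverse-event summaries pool induction with chemotherapy and maintenance on obinutuzumab alone; tables by phase of onset would be a cheap improvement

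*Protocol*

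**What the plan says.** Protocol 6.1 defines two exposures in sequence: "an induction treatment period (approximately 6 months) in which patients will receive Obinutuzumab and chemotherapy", then "a maintenance treatment period (approximately 24 months) in which patients will receive Obinutuzumab monotherapy".

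The safety variables in the Synopsis are "Incidence, nature, seriousness, severity and relatedness of all adverse events (AEs) and serious adverse events (SAEs"), with no mention of phase. The analysis text is as follows:

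- **Window.** Protocol 6.7.2 and SAP 3.3.1 use a single period, from the first obinutuzumab dose to 185 days after the last one or the start of a new anti-cancer therapy. Later events are collected if thought related.
- **Population.** SAP 3.1 and 3.3 use all enrolled patients.
- **Tables.** SAP 3.3.1 states: "Summary statistical tables including frequency counts and percentages and the number of adverse events will be produced". The dimensions named are mapped term, thesaurus level and CTCAE grade. The summary entry in SAP Appendix 2 is "Summary of Adverse Events and IRRs".
- **Repeats.** Protocol 6.7.2 counts a patient once per preferred term, with the worst grade, the earliest start and the latest stop. SAP 3.3.1 neither repeats nor withdraws this rule.
- **Causality.** Protocol Appendix 3.2 states: "For patients receiving combination therapy, causality will be assessed individually for each of the medicinal products".
- **Retrospective events.** Protocol 6.4.2 describes aggregate data with term, seriousness, relationship and duration as available. It names grade and onset date only among the extra prospective variables. Note h to Protocol Appendix 2 requires only the preferred term for events before consent.

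**The concern.** The safety objective concerns obinutuzumab, and maintenance is the only phase in which the drug is given without chemotherapy. A single percentage per preferred term over the whole course describes a mixture of two regimens. It does not show how much of, say, the infection burden arose alongside chemotherapy and how much on the antibody alone. Protocol section 4 itself names neutropenia and infections among the major safety events.

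The counting rule adds to this. A patient with an infection in induction and another under the same term in maintenance contributes one event with an induction start date. Even someone who later splits the summarised events by start date would then undercount maintenance.

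The plan treats phase and backbone as informative elsewhere. Response is assessed at mid and end of induction and during and after maintenance, questionnaire timing differs by phase, and effectiveness is examined by chemotherapy backbone. The adverse-event tables have neither split.

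**Working it through.** The documents give no adverse-event figure by phase, so there is none to reproduce. The inputs are the planned durations, the dosing table and N = 300.

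**1. Share of treatment in maintenance**
- Durations (Protocol 6.1): 6 + 24 + 12 months of follow-up = 42, which agrees with "For each patient, the study will consist of a period of 42 months".
- By time: 24 / (6 + 24) = 80%.
- By planned doses (Synopsis Table 1): induction is 3 + 5 = 8 doses with six cycles, or 3 + 7 = 10 with eight. Maintenance is 24 / 2 = 12. The share is 12/20 = 60% or 12/22 = 55%.
- Both shares apply to a patient who completes both phases.

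**2. What a pooled incidence reveals about maintenance**
- Suppose 120 of 300 patients have a given term at least once (40%; exact 95% CI 34.4–45.8%). This is an assumed figure.
- Counted once per patient, anywhere from none to all 120 may have had it in maintenance. That is 0/300 to 120/300, or 0% to 40% of enrolled patients.
- If only 240 entered maintenance (assumed), the range among entrants is 0% to 120/240 = 50%.
- A second illustration assumes independence and that everyone enters both phases. Rates of 20% in induction and 30% in maintenance give 1 − 0.80 × 0.70 = 44%. Rates of 40% and 6.7% give 1 − 0.60 × 0.933 = 44%. The table would be the same with a more than fourfold difference on monotherapy. The rates were chosen to show this and are not predictions.

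**3. Precision of phase-specific tables**

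The Clopper-Pearson method reproduces the protocol's 13% row: 39/300 gives 9.4–17.3%, width 7.9%. The documents do not say how many patients will enter maintenance; 240 to 300 is assumed.

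| True maintenance incidence | n = 240 | n = 300 |
|---|---|---|
| 10% | 6.5–14.5% | 6.8–14.0% |
| 20% | 15.1–25.6% | 15.6–25.0% |

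**4. Whether onset can be assigned**
- Consent comes after at least two cycles and no later than one year from the start of treatment.
- Maintenance runs from about month 6 to month 30. At the latest consent, 30 − 12 = 18 of 24 maintenance months (75%) are prospective, and onset dates are then collected as available.
- For a patient who consents during induction, every earlier event is an induction event even without a date.
- The ambiguous events are mainly undated ones in patients who consent after maintenance has begun, which can cover up to about 12 − 6 = 6 months of it.

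**The case against.** The strongest reply is that the objective is the safety of obinutuzumab in routine use, the labelled treatment is the whole sequence, and the study is declared exploratory and descriptive. Whole-course incidence is then a legitimate answer. This stands as a reason to keep the overall table. It is not a reason to report nothing by phase.

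A reader might also draw stronger conclusions that the documents do not support:

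- **That monotherapy safety cannot be read from the results at all.** Adverse events are listed by site, patient and study day, and prospective events carry dates as available. A partial post hoc split is possible. What is missing is a prespecified summary with a proper denominator.
- **That the timing of cytopenias is lost.** SAP 3.3.2 displays laboratory data by time and grades them by CTCAE, and haematology includes neutrophils and platelets. This partly covers cytopenias, though not as adverse-event incidence.
- **That the COVID-19 delay question is compromised.** Maintenance delay, its reason and its effect on PFS and POD24 are separate analyses in SAP 3.5. They do not depend on the adverse-event tables.
- **That a maintenance rate is diluted by patients who never start maintenance.** The plan reports no maintenance rate, so none is diluted. The denominator matters only when the new tables are built.
- **That 80% measures exposure generally.** It is a share of planned time only.

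Per-product causality helps, but it is a yes/no judgement and is not required for events before consent. The objection that retrospective grade and dates are incomplete is sound, and the new tables must allow for it.

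**Conclusion.** The point holds as a cheap improvement. In the text and output list that can be read, no summary table gives adverse-event incidence during obinutuzumab monotherapy, and the once-per-term rule in Protocol 6.7.2 hides recurrences in maintenance. On the planned durations, the phase without its own summary is 80% of treatment time and 55–60% of doses. A pooled incidence sets only an upper limit on the share of enrolled patients affected in maintenance.

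This rests on two conditions. First, the table templates in SAP Appendix 3 could not be seen, so a phase split at the second interim analysis cannot be excluded; SAP 3.3.1 and Appendix 2 give no sign of one. Second, the rates in the illustrations and the 240 to 300 patients entering maintenance are assumptions. POD24, its precision and the sample size are not affected.

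**What to change.** Keep the overall table. In SAP 3.3.1 and SAP Appendix 2, add tables of treatment-emergent events, serious events and infections by SOC and preferred term, set out as follows:

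1. **Phase of onset:** induction; maintenance; after the last dose to day 185 or new anti-cancer therapy, whichever is first.
2. **Denominator:** patients who entered the phase.
3. **Counting:** apply the once-per-term, worst-grade rule within each phase rather than across the whole course, and amend the wording carried in Protocol 6.7.2 to match.
4. **Undated events before consent:** assign to induction when consent preceded the first maintenance dose. Put the rest in a 'phase unknown' row, including those of patients who had already ended treatment before consenting.
5. **Grade:** show worst grade with a 'grade not collected' category, because grade is not required for retrospective events.
6. **Backbone:** tabulate induction by chemotherapy backbone, descriptively.

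The cost is a few extra tables, with no added patients, visits or procedures. The drawback is that grade will be incomplete and some events unassigned in the retrospective part. Because consent may come as late as one year, that part can include all of induction for some patients.

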3. PROTOCOL AMENDMENTS AND UPDATES

Any protocol amendments will be prepared by the Marketing Authorization Holder or designee.

Protocol amendments will be submitted to the Institutional Review Board (IRB)/Ethics Committee (EC) and to regulatory authorities in accordance with local regulatory requirements.

Approval must be obtained from the IRB/EC and regulatory authorities (as locally required) before implementation of any changes, except for changes that involve logistical or administrative aspects only (e.g., change in Site Operations Representative or contact information).

Substantial protocol amendments/updates so far: *Tracked in the section “Summary of changes” of the Protocol none.*

4. RATIONALE AND BACKGROUND

Background on Follicular Lymphoma

Non-Hodgkin's lymphomas (NHL) are a heterogeneous group of lymphoproliferative tumours with varying behaviour and treatment-response patterns (*Armitage 1993*).

NHL is the most common hematologic malignancy in adults. In 2008, over 66,000 new cases were reported in the United States, with more than 19,000 deaths.

In Italy, it has been estimated that one in every 44 males and one in every 62 females will develop NHL, and that one in every 106 and one in every 152, respectively for the two sexes, will die of the disease (*AIRTUM Working Group. 2009*).

The majority of NHLs (also known as malignant lymphoma) are of B-cell origin and are characterized by the expression of a membrane antigen, CD20, which is important in cell cycle initiation and differentiation (*Anderson et al. 1984*). NHL can be divided into aggressive and indolent NHL. Indolent NHLs are a heterogeneous group of malignant lymphomas and account for about one-third of all NHLs.

Follicular lymphoma (FL) is the second most common lymphoma and is the most common subtype of indolent B-cell lymphomas diagnosed in the United States and Western Europe, accounting for approximately 35% of all NHLs, and 70% of indolent lymphomas (*Swerdlow et al. 2008*). The median age of diagnosis is at 65 years and the incidence is slightly increased among relatives of persons with FL (*Goldin et al. 2009*).

FL associated with follicle centre B cells that typically contain the *BCL2* chromosome trans location t(14:18), leading to overexpression of the intracellular anti-apoptotic protein Bcl-2.

Patients with FL are usually at diagnoses at an advanced state of the disease. They generally present with asymptomatic lymphadenopathy, with waxing and waning present for years. Bone marrow involvement is present in 70% of patients, whereas involvement of other normal organs is uncommon. Less than 20% of patients present with B symptoms and also less than 20% of patients present with an increased serum lactate dehydrogenase (LDH) (*Freedman 2015*).

The clinical course of indolent NHL is characterized by remission and relapse (*Gallagher et al. 1986*). The disease initially responds to radiation and/or immunochemotherapy with conventional agents, but patients eventually suffer multiple relapses distinguished by increasing refractoriness and decreasing duration of response in subsequent lines of therapy. Patients with advanced-stage disease are not usually cured with conventional treatment and ultimately die from recurrent disease or treatment-related toxicity.

Patients who are diagnosed without symptoms can be observed without treatment (so-called watchful waiting) for several years. However, treatment is required when the patient presents with symptoms at diagnosis or develops symptoms during observation (*Izutsu 2014*).

Treatment modalities for FL include chemotherapy, radiotherapy and immunotherapy against CD20, and stem cell transplantation, but a standard treatment approach for FL has not been established.

For FL patients requiring treatment, immunochemotherapy with rituximab, a monoclonal antibody directed against CD20, plus chemotherapy has demonstrated improvements in response rates, progression-free survival (PFS), and overall survival compared with chemotherapy alone (*Hiddemann et al. 2005; Herold et al. 2007; Marcus et al. 2008; Salles et al. 2008*). Rituximab in combination with chemotherapy (e.g., CHOP [cyclophosphamide, doxorubicin, vincristine, and prednisone], CVP [cyclophosphamide, vincristine, and prednisone], or purine analogue-based schemes such as those with fludarabine or bendamustine) for newly diagnosed patients with advanced Stage III and IV disease requiring treatment is strongly supported by International Guidelines (*Dreyling 2009; Zelenetz et al. 2010*).

In addition to immunochemotherapy induction, randomized clinical trials have also demonstrated the benefit of maintenance rituximab in responding patients in both previously untreated and relapsed FL (*van Oers et al. 2006; van Oers et al. 2010; Salles et al. 2011*).

Currently, the first-line treatment for FL is rituximab in combination with chemotherapy, followed by maintenance therapy with rituximab every two months for two years, as demonstrated by results of the PRIMA study (*Salles et al. 2011*). This regimen had determined a satisfactory result in most of treated patients, with a 10-year progression-free survival of 51%.

Despite these encouraging results, therapy for FL is not curative and presents with a chronic course (i.e. remitting-relapsing), with progressively shorter remissions and with increased risk of developing a transformation of the disease, i.e. the transition from an indolent malignant lymphoma to a more aggressive type of lymphoma. Patients who have an early disease progression (within 24 months) will have a more aggressive course and a shorter survival, and will be treated with more therapeutic lines, than those patients without an early progression. The majority of patients will ultimately die from progressive disease. Therefore, the introduction of new agents that may potentially alter the natural history of the disease is of great interest.

Background on Obinutuzumab

Obinutuzumab is a recombinant monoclonal humanised and glycoengineered Type II anti-CD20 antibody of the IgG1 isotype. It specifically targets the extracellular loop of the CD20 transmembrane antigen on the surface of non-malignant and malignant pre-B and mature B-lymphocytes, but not on haematopoietic stem cells, pro-B-cells, normal plasma cells or other normal tissue. Glycoengineering of the Fc part of Obinutuzumab results in higher affinity for Fc γ RIII receptors on immune effector cells such as natural killer (NK) cells, macrophages and monocytes as compared to non-glycoengineered antibodies.

In nonclinical studies, Obinutuzumab induces direct cell death and mediates antibody dependent cellular cytotoxicity (ADCC) and antibody dependent cellular phagocytosis (ADCP) through recruitment of Fc_YRIII positive immune effector cells. In addition, *in vivo*, Obinutuzumab mediates a low degree of complement dependent cytotoxicity (CDC). Compared to Type I antibodies, Obinutuzumab, a Type II antibody, is characterised by an enhanced direct cell death induction with a concomitant reduction in CDC at an equivalent dose. Obinutuzumab, as a glycoengineered antibody, is characterised by enhanced ADCC compared to non-glycoengineered antibodies at an equivalent dose. In animal models Obinutuzumab mediates potent B-cell depletion and antitumour efficacy. Furthermore, treatment with Obinutuzumab was able to control tumour growth when vehicle- and rituximab-treated tumours were not controlled (Mössner *et al.* 2010).

Obinutuzumab has been evaluated in a wide-ranging program of clinical trials in patients with B-cell malignancies. Efficacy as monotherapy has been reported in patients with relapsed/refractory indolent and aggressive NHL (Salles *et al.* 2012; Salles *et al.* 2013) and in chronic lymphocytic leukemia (CLL) of B-cell origin (Cartron *et al.* 2014).

Improved outcomes have also been noted when Obinutuzumab has been added to chemotherapy in patients with B-cell NHL (Radford *et al.* 2013).

The Phase III GADOLIN trial tested the clinical efficacy of Obinutuzumab plus bendamustine followed by Obinutuzumab monotherapy in rituximab-refractory indolent NHL versus treatment with bendamustine alone. After a median follow-up time of 21.9 months in the Obinutuzumab plus bendamustine group and 20.3 months in the bendamustine monotherapy group, PFS was significantly longer with Obinutuzumab plus bendamustine (median not reached [95% CI 22.5 months-not estimable]) than with bendamustine monotherapy (14.9 months [12.8-16.6]; hazard ratio (HR) 0.55 [95% CI 0.40-0.74]; $p=0.0001$) (Sehn *et al.* 2016).

A phase III study (the GALLIUM trial) compared the efficacy and safety of induction with Obinutuzumab, as compared with rituximab, each combined with chemotherapy, followed by maintenance therapy with the same monoclonal antibody, in patients with previously untreated indolent NHL (follicular lymphoma or marginal-zone lymphoma) (Marcus *et al.* 2017). A total of 601 patients in each group were randomised. After a median follow-up of 34.5 months, Obinutuzumab-based chemotherapy resulted in a significantly lower risk of progression, relapse, or death than rituximab-based chemotherapy (estimated 3-year rate of PFS, 80.0% vs. 73.3%; HR for progression, relapse, or death, 0.66; 95% CI, 0.51 to 0.85; $p = 0.001$). Response rates were similar in the two groups (88.5% in the Obinutuzumab group and 86.9% in the rituximab group). At a median follow-up of 41 months (Hideman *et al.* 2017), PFS was superior for Obinutuzumab plus chemotherapy over rituximab-based chemotherapy (overall HR, 0.68; 95% CI, 0.54 to 0.87; $p = 0.0016$). At this follow-up, the median PFS has not yet been reached, and it is not expected to be reached based on statistical hypotheses. Therefore, it is expected that the GALLIUM study will improve the median PFS observed in the PRIMA study, in which patients received the same treatment scheme of that used in the control arm of the GALLIUM study (i.e. rituximab + chemotherapy followed by

maintenance therapy with rituximab). Furthermore, the evidence from the GALLIUM study has shown that patients with advanced FL (high or intermediate FLIPI score) treated with Obinutuzumab-based chemotherapy for 2 years have a reduction of 32% of risk of disease progression (*Marcus et al. 2017*). A further analysis (*Seymour et al, 2018*) of the progression of disease at 2 years (POD24) and its impact on overall survival (OS) has shown that treatment with Obinutuzumab plus chemotherapy was associated with a marked reduction of POD24 compared to rituximab-based chemotherapy and that POD24 was associated with poor prognosis, with mortality risk higher after earlier progression.

Overall, Obinutuzumab has an acceptable safety profile as emerged from clinical trials. The major safety events were infusion-related reactions (IRRs) and hematologic adverse events (AEs), primarily neutropenia and infections. IRRs were the most common AEs throughout all clinical trials (*Edelmann et al. 2016*). They comprised of various symptoms such as hypotension or hypertension, tachycardia, dyspnea, pyrexia, chills, nausea, vomiting, diarrhea, flushing and headache coinciding with drug infusion. However, IRRs mainly occurred during the first infusion and almost always resolved with slowing or interrupting the infusion and/or upon steroid administration. Incidences of IRRs in clinical trials range between 64 and 86%, the majority of reactions being described as grades 1 and 2. A relation between Obinutuzumab dose and intensity of the IRR was not observed. In the GALLIUM study (*Marcus et al. 2017*), adverse events of grade 3 to 5 were more frequent in the Obinutuzumab group than in the rituximab group (74.6% vs. 67.8%), as were serious adverse events (46.1% vs. 39.9%). The rates of adverse events resulting in death were similar in the two groups. The most common adverse events were infusion-related events that were considered by the investigators to be largely due to Obinutuzumab in 59.3% of patients and to rituximab in 48.9 % of patients.

Obinutuzumab (Gazyvaro[®]), in combination with chlorambucil, is indicated for the treatment of adult patients with previously untreated CLL and with comorbidities making them unsuitable for full-dose fludarabine based therapy. From October 2017, Obinutuzumab is also indicated, in combination with bendamustine followed by Obinutuzumab monotherapy, for the treatment of patients with FL who relapsed after, or are refractory to, a rituximab-containing regimen. Obinutuzumab has also received the approval from the European Medicines Agency (EMA) for use in combination with chemotherapy, followed by Obinutuzumab maintenance therapy in patients with previously untreated advanced follicular lymphoma.

